### 7.4. Serious Adverse Event (SAE)

A serious adverse event (SAE) is an AE occurring during any phase of the study (i.e., screening, admission, treatment, or follow-up) that fulfills one or more of the following criteria:

- Results in death
- Is immediately life-threatening
- Requires in-patient hospitalization or prolongation of existing hospitalization (more than 24 hours)

- Results in persistent or significant disability or incapacity
- Is a congenital abnormality or birth defect
- Is an important medical event that may jeopardize the subject or may require medical intervention to prevent one of the outcomes listed above

## 7.5. Identifying, Reviewing, and Reporting Adverse Events and Unanticipated Problems to the IRB

### Identifying

- To effectively identify all AEs (anticipated or unanticipated), [name] lab staff will follow laboratory and protocol specific SOPs, complete AE reporting forms for each subject as they arise, and maintain a database of all reported adverse events for each protocol by entering all AEs into REDCap within a timely manner. All stopping events or subject reported complaints/concerns will be documented via study notes during the study. Participants will be encouraged to contact us with any questions or concerns following the study visit.

### Reviewing

- The PI, study physician, and study team will also review AEs during internal audits of study documents in a cumulative fashion to identify any trends of safety concerns (see section [7.8 Internal Audits](#)). In the event of an SAE, the PI, study physician, DMC, and IRB will review the event as soon as possible.

### Reporting

- All adverse events will be recorded in REDCap in a timely manner consistent with reporting requirements. [name] lab staff will log all AEs in REDCap, and report AEs and unanticipated problems to the DMC and to the IRB as indicated by IRB guidance on Knowledge Base.

## 7.6. Expedited Adverse Event Reporting Requirements

### Serious Adverse Event— Reported Within 24 Hours

- Serious Adverse Events requiring expedited reporting within 24 hours will be reported to both the UW Health Sciences IRB and the ICTR DMC Manager within one working day as directed below. Confirmation that all appropriate parties were notified will be done at this time.

### Serious Adverse Event – Reported within 15 Days

- Serious Adverse Events requiring expedited reports in writing within 15 working days will be sent by the PI and study team.

## 7.7. Protocol Deviations

To effectively identify deviations from the IRB approved protocol, [name] Lab staff will maintain protocol checklists that are designed to not only minimize protocol deviations but to identify deviations when they do occur. Additionally, [name] Lab staff will conduct regular internal audits (see section [7.8 Internal Audits](#)) to identify deviations that may have been overlooked. All deviations will be logged on a Deviation Tracking Log and a database of deviations will be maintained in REDCap. The PI will review deviations as they are identified, and oversight committees will be notified according to their guidelines. The study team will implement corrective action plans when appropriate to address deviations.

## 7.8. Internal Audits

Regular internal audits will be conducted to ensure compliance and safety. Internal audits will occur on a quarterly basis. These audits could consist of full or partial review of study records, depending on

observed past compliance. Audits will be documented on Internal Compliance Review forms modified specifically for the study and will include review of the following:

- Personnel (e.g., ensure all personnel have the appropriate training)
- Documentation of IRB submissions and correspondence
- Informed Consent/HIPAA Authorization Forms
- Laboratory Aspects of the Trial
- Equipment Maintenance
- Communication and Correspondence with oversight committees
- Study Conduct
- Completion of Case Report Forms
- Adverse Events
- Protocol deviations

These internal audits will identify any unanticipated outcomes or trends, and [name] Lab staff can then notify the IRB of any new, common, or unanticipated adverse events, if applicable.

The results from internal audits (e.g., noncompliance, adverse event trends) will be discussed during regular lab meetings where team members can establish plans to prevent future issues.

## 7.9. Minimizing Research-Associated Risk

First and foremost, risks will be minimized by the prescreening procedures to determine preliminary eligibility, which includes thorough health history and MRI safety questionnaires (see section [4.3.1. Pre-Screening Subjects](#)) which will be verified by the subject's parent/guardian (if <18 years of age). Secondly, in-person anthropometric measurements and survey of pregnancy (see section [4.3.2. In-Person Screening](#)) will further establish safety for subject participation. This two-stage process should minimize risk prior to any study conditions being imposed on the participants.

Once enrolled as a subject and participation in the trials begins, we will monitor heart rate, blood oxygen saturation, blood pressure, end-tidal carbon dioxide, and subject comfort throughout the study visit (if applicable; see section [4.3.4.m. Subject Monitoring](#)). This data will be used to monitor the health of our participants and for research purposes.

Having only trained personnel performing the IV catheter placement under aseptic conditions will minimize IV catheter placement risk.

Screening each subject for cardiovascular disease and any blood clotting disorders will minimize intravenous catheter placement risk.

If a participant reports positive pregnancy, the study team will immediately end further screening procedures and will only state that the subject is not eligible without details as to the reasoning. This is done to protect the confidentiality of the pregnancy screening procedure (see section [4.3.2. In-Person Screening](#)).

Although we are extensively screening out subjects that have overt diabetes, the results of the experimental OGTT may produce results identifying that a subject may be diabetic which may indicate a clinical concern. The fact that insulin analysis will occur towards the end of the study (due to cost limitations with assay) means diabetic subjects will have completed all Aims of study. A diabetes finding does not pose further risk to the patient.

Using the standard exclusionary procedures to prevent subjects with hazardous metallic implants, cardiac pacemakers, or subjects who are pregnant will minimize the risks of MRI scanning. A standard safety screening form used for clinical MRI scanning will be used to exclude patients with hazardous metallic implants, cardiac pacemakers, or patients who are pregnant. In addition, all operators of the MRI equipment are trained in the proper use of hearing protection, padding, and subject monitoring. To minimize any discomfort, participants will be provided with disposable earplugs or headphones to wear during the procedure. These earplugs will protect their ears but still allow communication with the technician running the scan.

With constant monitoring by the study team under the supervision of Drs. [name] and [name], we will record and identify trends and report any significant problems to the IRB. We will compile an electronic record of any adverse events associated with each subject and will review these events as they occur. We will also review cumulative events to identify trends as well as approaches to stop trends and approach the IRB with appropriate protocol modifications.

### **7.9.1. Initial screening**

All subjects will be asked to complete an initial pre-screening, documenting physical activity, medical history, medications, and MRI safety (see section [4.3.1. Pre-Screening Subjects](#)). The questions are designed to immediately eliminate those subjects meeting exclusion criteria. A detailed initial screening script and survey is included in the formal IRB proposal. Potential subjects who are ineligible, or who decline to participate, will have their screening information deleted or destroyed.

During the in-person screening, if the subject is ostensibly ineligible (e.g. weight<94.5 lbs), we will stop the screening process immediately. The reason for stoppage will be documented. This will not be considered a deviation to the protocol.

Other studies in the PI's lab investigate the same subject population and utilize similar screening procedures. A subject recruited from another study can have their screening information from that study used for the purposes of this study to minimize subject burden. Any procedures that were not included in the other studies' screening process that are required for this study will be conducted. Screening information will be valid for 180 days.

### **7.9.2. Subject Monitoring**

Testing may include subject monitoring of heart rate, oxygen saturation, end tidal carbon dioxide, and blood pressure (if applicable; see section [4.3.4.m. Subject Monitoring](#)). With continuous monitoring, we can readily observe any adverse events in real time and move to stop procedures immediately and return to baseline conditions. In case of serious cardiovascular event, a defibrillator is located nearby all testing areas, and CPR certified staff is present during procedures. In the case of emergency, 911 will be contacted. Further, in the event of a "code" for procedures at the WIMR, the WIMR is now part of the UWHC Code response area such that emergency team response time is excellent.

### **7.9.3. Blood Sampling**

Blood sampling (not venipuncture or IV placement) will be performed only by research personnel that have had phlebotomy training. This training has encompassed the insertion, maintenance, and use of intravenous catheters. These personnel all have at least a bachelor's degree or higher health and/or physiology-related education in terms of academic preparation. We feel education and training of

personnel, and our positive track record over 10 years at UW performing similar invasive procedures, provide high confidence IV blood draws present a very low risk to subjects.

#### **7.9.4. Protecting the Confidentiality of Participant Data**

Risks to confidentiality will be minimized by keeping copies of the documents linking study assignment number and the participant's unique identifiers with the participant's informed consent in locked cabinets of the offices of [name]. Only subject numbers will be used for group assignment, data processing, and analyses. All data will be stored in locked cabinets in a secure lab, and electronic files are all stored on password-protected databases and computers.

Personal information such as name, gender, date of birth, and medication history will be stored in a locked file cabinet in a locked office in the PI's laboratory. Subject information will be coded to remove any personal identifiers during data analysis or research publications. Research oversight and regulatory groups may review study records.

Data will be stored as both hard copies and electronic files. Hard copy data collection forms will be locked in a file cabinet in the restricted-access laboratory area or in the Department of Neurology (cognitive testing files only). Electronic files that contain potential Protected Health Information (PHI) will be stored in REDCap, a secure web-based data management system, and/or a secure Box folder configured with the involvement of the UW-Madison HIPAA security officer. Electronic files will be HIPAA compliant and will use a subject ID instead of the subject's name. The raw MRI data will be stored on servers assigned to [name] and managed by the Departments of Medical Physics and Radiology and/or on encrypted external hard drives.

Blood samples may be analyzed for insulin and inflammatory markers externally to the study team (e.g. UW Primate Research Center). Samples analyzed at the UW Health Clinical Labs will be placed in the medical record of the subjects per UW Health policy. Samples analyzed at research labs (e.g. UW Primate Research Center) will remain coded such that the outside blood analysis team will not be provided any identifiers or means by which they could connect the blood samples to any individuals that have participated in the study.

### **7.10. Stopping Guidelines**

#### **7.10.1. Study Stopping Guidelines**

This study may be temporarily suspended or prematurely terminated if there is sufficient reasonable cause. Written notification, documenting the reason for study suspension or termination, will be provided by the suspending or terminating party to investigator, funding agency, and regulatory authorities. If the study is prematurely terminated or suspended, the PI will promptly inform the IRB and will provide the reason(s) for the termination or suspension. Circumstances that may warrant termination or suspension include, but are not limited to:

- Determination of unexpected, significant, or unacceptable risk to subjects
- Insufficient compliance to protocol requirements
- Data that are not sufficiently complete and/or evaluable

The study may resume once concerns about safety, protocol compliance, and data quality are addressed and satisfy the applicable regulatory authorities.

### 7.10.2 Subject Stopping Guidelines

Each intervention (i.e. study visit) will be terminated based on the following specific guidelines:

- If the subject wishes to stop
- If the subject complains of serious pain or discomfort
- If the subject is admitted to hospital for psychiatric distress
- If the subject complains of (related to MRI):
  - Discomfort
  - Anxiety
  - Claustrophobia
- If baseline glucose is  $\geq 126$  mg/dL and is not the result of non-compliance with fasting requirement (see [4.1.2. Exclusion Criteria](#))
- Any SAE occurring during study procedures

## 8. STATISTICAL CONSIDERATIONS

Covariates for all analyses include sex, age, adiposity, aerobic fitness, and education unless noted otherwise.

The overarching statistical approach uses multiple regression to determine whether IR is inversely associated with outcome measures in Aims 1 and 2 and to assess mediation in Aim 3. Mean/summed outcomes (total cognition, total CBF or CP) will be predicted by HOMA-IR, for example. Not only is a composite measure calculated as a mean more reliable than the subdomain scores, but averaging multiple measures of a single construct yields a more powerful hypothesis test than using variables individually (40), under conditions we expect to hold here. This approach avoids inflation of Type I error rate as each hypothesis test examines the relationship among single variables or composites, not among multiple subdomain measures. If the test of the mean or composite score is significant, then there is no increased Type I error rate incurred in subsequent subdomain/regional tests (41).

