**1. PROJECT SUMMARY**

One in five American adolescents are obese, and many of these patients exhibit some level of insulin resistance (IR). IR is associated with cerebrovascular disease, reduced memory, attention, and cognition, but how IR contributes to these in the course of adolescent brain development is unclear. The goal of this proposal is to investigate the extent and by which IR drives reductions in neurocognitive function and cerebral blood flow (CBF) in adolescents at elevated risk for poor brain and cerebrovascular health. We are testing the overall hypothesis that neurocognitive decline is linked to the severity of IR, as are reductions in brain perfusion, due to dysfunctional insulin signaling. We propose to study acute CBF control in healthy adolescents (12-18 years) across a range of IR (diabetes excluded) in collaboration with expert childhood neuropsychologists who lead a comprehensive cognitive testing protocol. Next, two complementary MRI methods (ASL and phase contrast MRI), along with a physiologic stressor to challenge CBF, will be used to test whether the impact of IR on brain macrovascular CBF and microvascular perfusion is regionally specific, with more negative effects in temporal and parietal lobes. These lobes are some of the initial brain areas to change in neurodegenerative diseases, and are involved in attention, memory, learning, and cognition. Finally, this study tests whether the degree of cognitive decline is linked to the CBF stress response and to severity of IR, and to what extent brain hypoperfusion mediates the IR-driven lower cognitive function. This study will provide the first comprehensive look at IR in adolescent brains, by utilizing extensive neuropsychological testing and state-of-the-art MR imaging, and drawing on interdisciplinary collaborations between developmental neuropsychologists, vascular physiologists, and pediatric endocrinologists. These studies are designed to uncover fundamental relationships between IR, neurocognitive function, and CBF in these blossoming adolescent brains. Exciting preliminary data support the aims—particularly uncovered by a physiologic insulin surge—signifying these findings will serve as a foundation for prospective, mechanistic studies to reduce the burden of IR and improve brain and cognitive health in this clinically important population.

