The **long-term** goal of this research program is to determine the influence of IR on brain development in adolescents through the relationships between neurocognition and cerebral blood supply. The **primary goal of the current project** is to quantify fundamental neurocognitive and cerebrovascular function in relation to the severity of IR. **Our central hypothesis** is that as IR worsens: **a**) subtle but meaningful neurocognitive declines emerge; **b**) regional brain perfusion is reduced primarily in areas linked to learning and memory *despite* preserved resting global cerebral blood flow (CBF); **c**) acute insulin surges exacerbate regional hypoperfusion, and **d**) cognitive scores will be lower, mediated in part by insulin-stimulated hypoperfusion.

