##### 3.1.2. Preliminary Data

Pilot data indicate similar brain and hippocampal volumes between groups (2.93 vs 2.84 mm^3). Cognitive testing results did not differ significantly between groups. However, episodic memory, executive function, and attention, as well as total composite cognition scores were all quantitatively lower in adolescents with high IR. Notably, these smoldering decreases in cognition are directly correlated to HOMA-IR. Collectively, these data suggest brain structure remains intact at this stage, yet fundamental memory and attention measures are declining in relation to worsening insulin resistance.

#### 3.2. Aim 2

To test the hypothesis that adolescents with higher IR:

- a) exhibit intact resting global macrovascular CBF but reduced microvascular perfusion in key brain areas involved in cognition, memory, and learning
- b) will exhibit further perfusion reductions in response to an endogenous insulin surge in contrast to increased perfusion in healthy adolescents.

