### 8.1. MRI Data Processing

Standard and validated tools will be used for image processing. The research team is expert in analyzing brain imaging data and have published several studies focused on MRI-derived blood flow-based measures.

Maps representing gray matter probability and cerebral blood flow will be generated using SPM, FSL, or similar software. Scans will be processed using the most up to date and recommended processing scheme, including methods previously used by our research group and collaborators.

We expect to use standard viewing software (Advanced Workstation 4.3, GE Healthcare) for magnetic resonance angiography and phase contrast data, in addition to

- 1) MIMICS and EnSight, commercial software packages commonly used in 4D flow visualization and
- 2) MatLab-based software for quantitative analysis of 4D data sets

Quantitative data from two 4D multi venc flow acquisitions will be available. The data includes:

- 1) Quantitative blood flow values (peak and mean flow, peak and mean velocity, pulsatility and resistance index) of 4D PC
- 2) Quantitative morphological data (vessel diameter) of:
  - a. Standard magnetic resonance angiography techniques
  - b. 4D PC

### 8.2. Aim 1

Composite scores will be computed by calculating and averaging z-scores within each cognitive domain. Composite total cognitive scores will be predicted from HOMA-IR and the covariates. Pilot data yielded a partial correlation of -0.6 between HOMA-IR and the total cognitive score. A one-tail test of the population correlation coefficient with a Type I error rate of 0.05 requires a sample size of **N=13** to yield power of 0.80. If this composite score test is significant, similar analyses will be performed to examine the relationship between HOMA-IR and individual cognitive ability subdomain scores.

### 8.3. Aim 2

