#### 8.3.3. Aim 2B

The change in CVC ( $\Delta\text{CVC}$ ) will be predicted from HOMA-IR and the covariates, where

$$\Delta\text{CVC} = (\text{peak CVC during OGTT}) - (\text{resting CVC})$$

Pilot data indicate the average correlation between HOMA-IR and  $\Delta\text{CVC}_{\text{MICRO}}$  of  $-0.42$ , so a one-tailed test of the partial correlation will yield power of 0.80 with a sample size of **N=31**, with Type I error rate of 0.05. We plan to assess numerous regions of interest (ROIs) linked to executive functions and memory, including frontal, temporal, and parietal regions (e.g. middle, medial, and superior frontal gyri, anterior cingulate, hippocampus, middle and superior temporal gyri, posterior cingulate, precuneus), as well as ROIs *with less involvement* in memory or executive functions (e.g. precentral and postcentral gyri, occipital cortex).  $\Delta\text{CVC}_{\text{MICRO}}$  is only predicted from HOMA-IR within an ROI, not between, to limit the number of comparisons and therefore limit the false discovery rate.

For  $\Delta\text{CVC}_{\text{MACRO}}$ , up to 11 extra- and intra cranial arteries will be studied (basilar, 2 ACA, 2 MCA, 2 PCA, 2 vertebral, and 2 ICA; dependent on individual anatomy). Total CBF will be calculated, where

$$\text{CBF}_{\text{TOTAL}} = \text{CBF}_{\text{BASILAR}} + \text{CBF}_{\text{ICA-Right}} + \text{CBF}_{\text{ICA-Left}}$$

Pilot data indicate that the average correlation between HOMA-IR and MCA perfusion during OGTT is -0.796, so that a one-tailed test of the partial correlation will yield the power of 0.80 with a sample size N=6, with Type I error rate of 0.05. For all of Aim 2, if either total CVC test is significant (micro or macro), similar regression analyses will be performed to examine the mediating effects of  $\Delta$ CVC between HOMA-IR and individual ROI (micro) or artery (macro)  $\Delta$ CVC values.

#### 8.4. Aim 3

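### The composite gate in Section 8 does not protect regional and subdomain tests when two or more members are null beside affected ones, and the regional-specificity question has no between-region contrast

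*Combined protocol and SAP*

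**What the plan says.** Section 8 sets out a two-step approach. A mean or composite is tested first. If it is significant, the members are tested, and "there is no increased Type I error rate incurred in subsequent subdomain/regional tests".

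The gate is then used in each aim:
- **Section 8.2 (Aim 1):** after a significant total cognitive score, "similar analyses will be performed to examine the relationship between HOMA-IR and individual cognitive ability subdomain scores".
- **Section 8.3.3 (Aim 2):** "if either total CVC test is significant (micro or macro), similar regression analyses will be performed", for regions of interest (ROIs) on the micro side and up to 11 arteries on the macro side. The rest of that sentence describes these follow-ups as examining mediating effects of ΔCVC.
- **Section 8.4 (Aim 3):** a significant result at rest or under OGTT opens the analyses by cognitive domain.

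On regions, the Project Summary says the study will test "whether the impact of IR on brain macrovascular CBF and microvascular perfusion is regionally specific, with more negative effects in temporal and parietal lobes". The central hypothesis in Section 2.1 is that "regional brain perfusion is reduced primarily in areas linked to learning and memory". Aim 2 in Section 3.2 expects "reduced microvascular perfusion in key brain areas involved in cognition, memory, and learning". Section 8.3.3 will assess "numerous regions of interest (ROIs) linked to executive functions and memory, including frontal, temporal, and parietal regions", naming nine examples, plus three examples of regions with less involvement in those functions. It then says that micro ΔCVC "is only predicted from HOMA-IR within an ROI, not between, to limit the number of comparisons and therefore limit the false discovery rate". It mentions the false discovery rate but names no procedure that controls it.

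**The concern.** There are two separate issues.

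**Error rate.** A composite gate stops false member findings only by staying shut. If some members are truly affected, they open it, and each null member is then tested at the full unadjusted level. A reader who relies on Section 8 would take every regional, arterial or subdomain p-value below 0.05 as error-protected, although that holds only in some configurations.

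**Specificity.** Whether IR affects some regions more than others is a question about a difference between slopes. Separate within-region tests do not estimate that difference. A significant region beside a non-significant one does not show that the two differ, even if no region is null. Without a contrast, specificity would be read from which p-values fall below 0.05.

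**Working it through.** **1. The plan's own figure.** Section 8.3.2 gives N=55 for r=−0.324, one-sided 0.05, power 0.80. Using the noncentral t with df=N−2, the noncentrality is √55 × 0.324/√(1−0.324²) = 7.416 × 0.324/0.946 = 2.54, and the power is 0.806. The stated N is reproduced and is not in dispute.

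**2. When the gate protects.**
- All members null: a false member finding needs a false gate, so the familywise error is at most about 0.05.
- One null: only one hypothesis can be falsely rejected, at 0.05.
- k nulls, gate opened by affected members, independent tests: 1−0.95^k, which is 0.0975 (k=2), 0.143 (k=3) and 0.265 (k=6).

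Positive correlation lowers these figures, so the whole procedure was simulated.

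**3. Simulation of the gated procedure.** From the plan: N=55; six covariates for CVC analyses (five in Section 8 plus intracranial volume), so residual df=55−2−6=47; 12 named ROIs; total r of −0.324 (Section 8.3.2) or −0.42 (Section 8.3.3). Inferred: one-sided 0.05 per ROI, because the follow-ups are described as similar regressions. Assumed: the total is the mean of the 12 ROIs, the residuals are equicorrelated, and the null counts. Chance of at least one false ROI at total r=−0.42:

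| Null ROIs of 12 | corr. 0.2 | 0.4 | 0.7 | 0.9 |
|---|---|---|---|---|
| 12 | 0.048 | 0.048 | 0.050 | 0.050 |
| 1 | 0.051 | 0.050 | 0.048 | 0.051 |
| 2 | 0.095 | 0.088 | 0.082 | 0.071 |
| 3 | 0.137 | 0.121 | 0.102 | 0.079 |
| 6 | 0.236 | 0.207 | 0.150 | 0.101 |

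Results at r=−0.324 are close to these. Over both values and repeat runs the ranges are 7–10%, 8–14% and 10–25% for 2, 3 and 6 nulls. Holm after the gate gave 0.051 or less, within simulation error of 0.05.

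The other families behave alike. For 11 arteries gated on basilar plus both ICAs, the figures are 5% (1 null), 7–9% (2) and 9–17% (4). That run used r=−0.42, which is the micro pilot value; the macro value in Section 8.3.3 is −0.796. For the eight cognitive abilities of Table 1 (r=−0.6, five covariates, correlation 0.2–0.7) they are 5% (1 null) and 8–10% (2).

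**4. Specificity with no null region.** Let all 12 ROIs have the same true effect, set so that the total has the plan's r. With correlation ρ, the mean of 12 has residual variance v=(1+11ρ)/12. The slope per residual SD is b=r√v/√(1−r²), and each region has correlation b/√(1+b²). For a total of −0.324 and ρ=0.2: v=0.267, b=−0.177, regional r=−0.174. For ρ=0.9: v=0.908, b=−0.326, regional r=−0.310.

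| Pattern, gate open | Frequency |
|---|---|
| Significant and non-significant ROIs together, total r=−0.324 | about 22–74% |
| The same, total r=−0.42 | about 12–91% |
| Some target ROI significant and no comparison ROI significant (9 target, 3 comparison) | about 0.4–17% |

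The higher figures belong to the lower correlation. A mixed set of verdicts is therefore weak evidence that regions differ.

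**The case against.** The strongest defence is that these are gated follow-ups in a study that Section 4.1.1 describes as giving pilot data for later work, that the gate is valid under the complete null, and that Section 8.3.3 declines between-region testing on purpose to limit comparisons. Much of this stands. The composites are tested as planned, and with two nulls the error is at most about 10%. But limiting comparisons does not account for leaving out a contrast, since target minus comparison is one test. Nor does it make the unconditional sentence in Section 8 correct.

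Several stronger readings are tempting and are not supported:
- **That the less involved regions are null.** Less involvement in memory or executive function is not absence of a perfusion effect. The plan names no null region. Its wording is only compatible with a mix.
- **That a formal hypothesis goes untested.** The Aim 2 hypotheses in Section 3.2 do not themselves claim a between-region difference. The undertaking to test specificity is in the Project Summary.
- **That a clean but false specificity pattern would be common.** Mixed verdicts are common, but significant target regions with no significant comparison region are much rarer.
- **That Section 8.3.3 contradicts the Project Summary on lobes.** A list of regions to assess may be wider than the lobes where larger effects are expected. The sets need naming only if a contrast is run.
- **That a macro result is meant to open the ROI family.** The either-test wording in Section 8.3.3 permits this reading but does not state it.

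**Conclusion.** Both parts hold in limited form. The Section 8 statement is too broad: it is correct with all members null or exactly one null, and otherwise the error can exceed 0.05. The size depends on null counts and correlations that the documents do not give, and very high correlation shrinks the excess. Part two needs no assumption about nulls: the plan as written cannot answer the specificity question in the Project Summary, because Section 8 contains no HOMA-IR-by-region term or difference contrast. The composite tests, N=55 and the formal Aim 2 hypotheses are unaffected. This should be corrected before analysis, but it is a matter of wording and secondary analyses.

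**What to change.** 1. **Section 8.** Limit the Type I statement to the complete null, or delete it.
2. **Gates.** In Section 8.3.3, state that the micro total opens only the ROI family and the macro total only the artery family. In Section 8.4 the rest and OGTT tests both lead to the same cognitive domains, so state that each opens only the domain analyses for its own mediator. Also say what the Section 8.3.3 follow-up model is: the text speaks of mediation and not plainly of the HOMA-IR slope on each ROI or artery.
3. **Families.** Fix the ROI list and apply Holm within each family, or label the follow-up results exploratory. The cost of Holm is power. At its worst case for 12 tests (0.05/12=0.0042), a region whose own r is −0.42 falls from 0.92 to 0.66, and one at −0.324 from 0.75 to 0.36. Under equal effects the regional r is smaller than the total's, so power would be lower still.
4. **Specificity.** Either make no such claim, or name the region sets (the Project Summary gives temporal and parietal; Section 8.3.3 also lists frontal) and prespecify one secondary contrast. This is the target-set mean minus the comparison-set mean of standardised regional CVC or ΔCVC, regressed on HOMA-IR and the same covariates. Standardising matters: with equal correlations of −0.324 but a comparison-set SD 0.6–0.8 of the target's, the raw contrast would reject in about 8–42% of trials (assumed set correlation 0.4–0.9).

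The contrast has limited power. At two-sided 0.05 and assumed set correlation 0.4–0.7, it is 77–96% for −0.42 against 0 and 53–81% for −0.324 against 0. It falls to 30–52% and 12–20% if the comparison set has r=−0.20. A non-significant contrast would not show that regions are alike. No new data are needed.
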